16.5 Investigator Responsibilities41

LIST OF ABBREVIATIONS

| | |
|--------------|---|
| AE | Adverse event |
| CFR | Code of Federal Regulations |
| CRF | Case report form |
| DMC | Data Monitoring Committee |
| DSMB | Data Safety Monitoring Board |
| FDA | Food and Drug Administration |
| GCP | Good Clinical Practice |
| HIPAA | Health Insurance Portability and Accountability Act of 1996 |
| ICF | Informed consent form |
| ICH | International Conference on Harmonization |
| IEC | Independent Ethics Committee |
| IRB | Institutional Review Board |
| PI | Principal Investigator |
| SAE | Serious adverse experience |
| NSAID | Non-steroidal anti-inflammatory drugs: also known as “NSAIDs”; medication used to treat pain or swelling. |
| OA | Osteoarthritis |

PROTOCOL SYNOPSIS

| | |
|-----------------------------|--|
| TITLE | Long-term Management of “Younger, Active” Patients with Pain from Early Knee Osteoarthritis with Synvisc-One (hylan G-F 20) |
| SPONSOR | [name], University of California San Francisco |
| FUNDING ORGANIZATION | Genzyme |
| NUMBER OF SITES | 1 |
| RATIONALE | 
The objectives of the study are to assess the effectiveness, duration of symptom relief, improvements on activity level and safety of one or more hylan G-F 20 injections for symptomatic early knee osteoarthritis (OA) treatment in younger, active patients over a three-year period.
 
 •From a pain management perspective, reduction of knee pain knee pain will target a Patient Acceptable Symptom State (PASS) •Repeated hylan G-F 20 treatment will be allowed as necessary to maintain patients in PASS throughout the duration of the study period. |
| STUDY DESIGN | 
Typically viscosupplementation is considered an intervention for knee osteoarthritis in older patients who are less active. Many young active patients can also develop knee osteoarthritis after trauma or surgery or for congenital reasons. Treatment of these patients commonly are steroid injections which have more biologically detrimental effects for cartilage compared to viscosupplementation. This study aims to study use of viscosupplementation for young individuals who are active. Synvisc One injections, which are a single injection, will be used to determine effectiveness of reducing pain and maintaining an active healthy lifestyle for younger patients aged 30-50 years old.
 
This study, for research purposes only, will be an open label longitudinal cohort study with natural history over 3 years. Subjects
 |

| | |
|----------------------------------|--|
| | 
enrolled in the cohort will have baseline functional testing performed including a motion gait analysis, 12 minute walk test, and 3-day accelerometer data. Subjects will receive a single 6 mL intra-articular injection of hylan G-F 20 in the target knee at baseline. All ongoing treatments will be monitored at 6-month intervals over the 3-year duration of the study. Patients can receive any other conservative treatments (e.g., oral medications, physical or other therapy, acupuncture, etc., except other injection treatments) and current treatments will be documented during each patient encounter. An initial injection of hylan G-F 20 will be injected in the symptomatic knee using a standard supine lateral approach using a 20-gauge needle. A face-to-face follow up visit will be carried out 6 months after first injection with additional face to face meetings every 6 months thereafter unless the subject requires an additional injection of hylan G-F 20. Hylan G-F 20 treatments can be administered up to three times each year during the study duration. After each injection, follow up measures will be carried out using secure e-mail or phone contact at 6 weeks, 12 weeks, 18 weeks after each in-office evaluation or injection. Follow up will consist of WOMAC, Lysholm score, and Tegner score. Patients may return for retreatment of hylan G-F 20 if symptoms recur after at least 4 months following their previous injection and they meet the inclusion criteria for pain levels on the following WOMAC questions A1 (How much pain have you had walking on a flat surface?), C8 (How much difficulty have you had going down the stairs?), C9 (How much difficulty have you had when going up the stairs?), C10 (How much difficulty have you had when getting up from a sitting position?) and/or C23 (How much difficulty have you had while doing heavy household chores?). Inclusion criteria for pain level is defined by selecting moderate, severe, or extreme on all questions A1, C8, C9, C10 and/or C23. Those subjects who select mild or no pain levels on any of A1, C8, C9, C10 and/or C23, will not meet the criteria for WOMAC pain level and retreatment. Patients requiring three injections of hylan G-F 20 in 4 months or less will be allowed to exit the cohort after their six-month follow up following the third injection. Otherwise, patients will be followed until they reach the 3-year follow up, or drop out for other injection treatments or surgical treatment. Therefore, patients would potentially be able to receive up to 9 injections during the 3-year study.
 |
| 
PRIMARY OBJECTIVES
 | 
Specific Aim 1: To identify whether injection of 6 mL hylan G-F 20 decreases pain over 26 weeks in young (ages 30 to 50 years) active patients with symptomatic primary osteoarthritis of the knee not treated previously with hylan G-F 20.
 |

| | |
|--|---|
| 
SECONDARY OBJECTIVES
 | 
Specific Aim 2: Though symptoms can be improved for periods up to 6 months, pain symptoms can recur. The effect of repeated treatments of hylan G-F 20 will be studied.
 
Specific Aim 3: To identify the effects of treatment with hylan G-F 20 on activity levels (using objective activity measures utilizing accelerometer and Physical Activity Enjoyment Scale (PACES) and quality of life scores (WOMAC, SF-12) comparing baseline to treatment at 3 months.
 
Specific Aim 4: To understand the natural history of conservative treatment on this cohort of patients over a 3 year period.
 |
| 
NUMBER OF SUBJECTS
 | 
150
 |
| 
SUBJECT SELECTION CRITERIA
 | 
Inclusion Criteria:
 
Male or female patients aged 30-50 years
 
History of symptomatic unilateral primary or secondary knee OA for more than 6 months
 
Signed written informed consent
 
Radiographic evidence of Kellgren-Lawrence Grade I or II OA of the target knee
 
Body Mass Index (BMI) < 30 kg/m²
 
Activity criteria (Tegner score > 3)
 
Continued target knee OA pain despite conservative treatment ≥ 3 months (e.g., weight reduction, physical therapy, analgesics)
 
Willing to withhold intake of NSAIDs (including COX-2 inhibitors) and analgesics, for a washout period of minimum 3 days up to 21 days prior to baseline visit (depending on medication)
 
Willing to discontinue prohibited treatments and medications throughout study period
 
Baseline inclusion criteria
 
 • Completed OA medication washout period • Target knee pain 4-8 (0-10 NRS) during most painful knee movement (Worst Knee Pain) • If female, must have had a negative urine pregnancy test and |

used a medically acceptable form of contraception for at least 1 month prior to baseline and agree to continued use of contraception for the duration of the study. Otherwise, females must be surgically sterile, or postmenopausal (as documented in medical history) for at least 1 year. The fetal safety profile for G-F 20 is unknown. Pregnancy will affect the individual's regular activity levels. Females who become pregnant during the study will be excluded from the study. Subjects who become pregnant will be followed up by telephone every 3 months to check for any adverse effects. They will also be recommended to follow routine obstetric visits. Males should be able to father children as it has no expected effects on activity levels.

Exclusion Criteria: Known allergy to hylan G-F 20 or any of its components, or to avian proteins, eggs, feathers, down, or poultry
 Clinically apparent tense effusion or other acute inflammation of the target knee at baseline
 History of target knee viscosupplementation treatment
 History of major surgery for OA in target knee including arthroplasty or tibial osteotomy
 Arthroscopic surgery or intraarticular steroid injection in target knee within six months of baseline visit
 Significant (as judged by the Investigator) alignment deformity of target knee
 Ipsilateral symptomatic OA of hip or ankle; contralateral symptomatic OA of hip, knee, or ankle

History of:
 Septic OA of any joint
 Inflammatory arthropathy such as RA, gout, pseudogout, lupus, crystalline in-inflammatory arthropathy
 Active infection of lower extremity
 Known significant acute and/or concurrent medical disease including, but not limited to current malignancy, history of transplant surgery, congestive heart failure, significant unstable cardiovascular disease, renal hepatic pulmonary, endocrine, metabolic, or GI condition
 Any known contraindication to acetaminophen
 Venous or lymphatic stasis in either leg
 Peripheral vascular disease
 Patient has been prescribed chronic opioid analgesics at time of baseline visit
 Concurrent multi-system or multi-limb trauma
 Patient plans to become pregnant during study period

| | |
|--|--|
| | 
Patient plans to move significantly out of area, have surgery, or initiate or cease other OA treatments
 
Knee pain improves during washout period
 
Workman's Comp patient
 |
| TEST PRODUCT, DOSE, AND ROUTE OF ADMINISTRATION | 
Synvisc G-F 20 will be injected in the symptomatic knee using a standard supine lateral approach using a 20-gauge needle. Patients will be treated at baseline and followed out to three years. Patients may return for retreatment as early as 4 months post their prior injection if they meet the retreatment criteria pain levels for Worst Knee Pain. If the subjects need another injection, the follow-up cycle will restart at Visit 1 and the subject will be seen every 6 months and followed-up for 3 years.
 |
| CONTROL PRODUCT, DOSE AND ROUTE OF ADMINISTRATION | N/A |

| | |
|---|--|
| 
DURATION OF SUBJECT PARTICIPATION AND DURATION OF STUDY
 | 
Patients may return for retreatment as early as 4 months post their prior injection if they meet the retreatment criteria pain levels for Worst Knee Pain. If the subjects need another injection, the follow-up cycle will restart at Visit 1 and the subject will be seen every 6 months and followed-up for 3 years.
 
Approximate Time Requirements:
 
 • Baseline Screening: Informed Consent, Physical exam, patient questionnaire, injection, X-ray, walk test (Approx. 2 hours) and accelerometer test (3 days) • 6 months after injection: Physical exam, patient questionnaire, walk test (Approx. 1 hr) and accelerometer test (3 days) • 12 months after injection: Physical exam, patient questionnaire, walk test (Approx. 1 hr) and accelerometer test (3 days) • 18 months after injection: Physical exam, patient questionnaire, walk test (Approx. 1 hr) and accelerometer test (3 days) • 24 months after injection: Physical exam, patient questionnaire, walk test (Approx. 1 hr) and accelerometer test (3 days) • 30 months after injection: Physical exam, patient questionnaire, walk test (Approx. 1 hr) and accelerometer test (3 days) • 36 months after injection: Physical exam, patient questionnaire, walk test (Approx. 1 hr) and accelerometer test (3 days) • 15 min email or phone contact at 6, 12, and 18 weeks post each injection and clinic visit (total 4.5 hrs) 
Total time for the study will be approximately 8 clinical hours over 3 years, 21 days for the accelerometer test and 4.5 hrs of email/phone contact.
 |
| 
CONCOMMITANT MEDICATIONS
 | 
Allowed: Patients can receive any other conservative treatments (e.g., oral medications, physical or other therapy, acupuncture, etc., except other injection treatments) and current treatments will be documented during each patient encounter.
 
Prohibited: Since Synvisc is an elastoviscous fluid device injected directly into the knee joint, it does not interfere with any medicine that your physician recommends, including pain relievers and anti-inflammatory drugs.
 |
| 
EFFICACY EVALUATIONS
 | 
Efficacy will be measured and evaluated using data from the following assessments: KOOS, Lysholm, SF-12, WOMAC, and Accelerometer™.
 |

| | |
|--|---|
| PRIMARY ENDPOINT | 
The primary endpoint for the study will be analyzed using a responder analysis. The proportion of responders following injection within the 6 months following the baseline injection will be calculated based on Worst Knee Pain scores ≤ 3 on a 0-10 pain scale, which is a threshold consistent with other similar studies (Tubach 2005, Bellamy 2010). The primary endpoint is defined as non-inferiority of the proportion of responders in our study relative to an external criterion for the responder proportion (Bellamy 2010).
 |
| SECONDARY ENDPOINTS | 
Survival analysis statistics will be performed to assess duration of benefit from the hylan G-F 20 injections over time. A specific timeframe of interest will be the initial 6 months of treatment following the second and any subsequent hylan G-F 20 injection. Changes from baseline to three months post-treatment in activity levels (using objective activity measures utilizing accelerometer and Physical Activity Enjoyment Scale) and quality of life scores (WOMAC, SF-12) will be determined. We will examine the time courses of longitudinal measures of pain score, activity level, and quality of life over the entire three-year span of the study.
 |
| SAFETY EVALUATIONS | 
The repeat treatment phase evaluated the safety profile of a second injection of Synvisc-One. One hundred and sixty patients were treated during this phase of the study, of which 77 patients received a second injection of Synvisc-One. These patients were followed for 4 weeks and out of 77 patients, only 4 (5.2%) experienced device-related AEs in the injected knee. All such events were mild to moderate and were treated symptomatically. Patients who developed injected knee AEs during the initial phase of the study, and who subsequently received repeat treatment, did not experience injected knee AEs upon repeat exposure to Synvisc-One.
 |
| PLANNED INTERIM ANALYSES | 
There is no interim analysis planned. Serious adverse events will be monitored by the committee on an ongoing basis throughout the study.
 |

| | |
|---|---|
| 
STATISTICS Primary Analysis Endpoint
 | 
The primary endpoint for the study will be analyzed using a responder analysis. The proportion of responders following injection within the 6 months following the baseline injection will be calculated based on Worst Knee Pain scores ≤ 3 on a 0-10 pain scale, which is a threshold consistent with other similar studies (Tubach 2005, Bellamy 2010). The primary endpoint is defined as non-inferiority of the proportion of responders in our study relative to an external criterion for the responder proportion (Bellamy 2010). Bellamy demonstrated in his paper from 2007 (table 3) that a BLISS response at any time during the study was achieved in 70% receiving appropriate care and Hylan G-F 20 and only in 38% of patients receiving appropriate care ($P < 0.0001$). We propose a non-inferiority delta of 20% relative to this external criterion, and thus the primary endpoint will be tested by a test of our sample proportion (p) with null hypothesis $H_0: p < 0.50$ vs. alternative hypothesis $H_1: p \geq 0.50$. This test will be performed using the Wilson-Agresti method for testing a single binomial proportion at a one-sided significance level of 0.025 (i.e. non-inferiority will be satisfied if the 95% Wilson-Agresti (REF BROWN ET AL 2001) interval for the proportion of responders excludes the null rate of 0.50).
 |
| 
STATISTICS Secondary Endpoints
 | 
For subsequent injections, duration of response over time and median duration of response will be estimated using survival analysis techniques. Inference for activity levels and quality of life will focus on changes from baseline to 3 months. We will examine the time course for the longitudinal data on pain score, activity level, and quality of life measures across the three years of the study using mixed effects models.
 |
| 
Rationale for Number of Subjects
 | 
Power Calculation
 
Bellamy demonstrated in his paper from 2007 (table 3) that a BLISS response at any time during the study was achieved in 70% receiving appropriate care and Hylan G-F 20 and only in 38% of patients receiving appropriate care ($P < 0.0001$). A power calculation using a one-sample comparison of proportion with hypothesized value sample size was performed to determine non-inferiority to the 70% results quoted by Bellamy. Power calculations were measured using STATA's SAMPSI calculator. If we postulate a 20% non-inferiority limit (i.e. that at least 50% of patients receiving G-F 20 will achieve a BLISS response), the sample size required to have 90% power and
 |

| | |
|------------------------------------|--|
| | 
$\alpha=0.025$ to show non-inferiority at 50% would be 70. For a 10% non-inferiority limit with 90% power and $\alpha=0.025$, the required sample size is 274, and for 15% non-inferiority limit with 90% power and $\alpha=0.025$, it is 124 patients. These numbers do not allow for dropouts, therefore, we intend to recruit 150 subjects to account for dropout.
 
Conservatively assuming a 20% rate of drop-out, the resulting sample size of $n=120$ has better than 90% power (one sided test with $\alpha=0.025$) to show non-inferiority assuming the true responder rate is 65% (i.e. not quite as high as the 70% external reference).
 |
| 
DATA MANAGEMENT PLAN
 | 
Data management and analysis for the study will be performed by the Biostatistics Consulting Unit (BCU) of UCSF’s Clinical and Translational Science Institute (CTSI). Data will be stored on a HIPAA-compliant server. The server room has state-of-the-art environmental controls and security features and is protected by a firewall and anti-virus software.
 |

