2.1 Primary Objective

There are two primary objectives to this study:

Specific Aim 1: To identify whether injection of 6 mL hylan G-F 20 decreases pain over 26 weeks in young (ages 30 to 50 years) active patients with symptomatic primary osteoarthritis of the knee not treated previously with hylan G-F 20.

Specific Aim 2: Though symptoms can be improved for periods up to 6 months, pain symptoms can recur. The effect of repeated treatments of hylan G-F 20 will be studied.

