- **Duration of response:** Using Kaplan-Meier survival analysis techniques, we will estimate the probability of duration of response over time curve (survival curve) and its confidence limits and also the median duration time and confidence interval. Duration of response analyses will be conducted for the initial injection and also in the subset of patients that receive a follow-up injection.

- **Activity levels and quality of life:** We will estimate the average change and corresponding confidence limits from baseline to 3 months in each of the activity level measures (accelerometer test, walk test, Physical Activity Enjoyment Scale) and the quality of life measures (WOMAC, SF-12). The confidence intervals will be constructed using one sample t-distributions; in the event of strongly skewed measures, we will either use bootstrapping or transformation to construct more accurate intervals. The average change and the endpoints of the confidence intervals can be referenced to external clinically important improvements for comparison.

- **Long term outcome:** We will examine the time course for the pain score, activity level, and quality of life measures across the three years of the study. Estimates and confidence intervals will be derived using mixed effects linear models. Specifically, for each longitudinal outcome measure, we will model it as a function of the (categorical) time point. Intrasubject correlation will be accommodated by either a compound symmetry, autoregressive, or general covariance structure depending on best fit according to BIC. In the event of very non-normally distributed outcomes, we will employ normalizing transformations prior to the analysis. These analyses will be conducted using the Mixed procedure in SAS.

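### Aim 2 asks about repeat treatment when improved pain recurs, but recurrence is undefined and the planned pooled analysis of everyone re-injected can mix relapsers with subjects who never improved

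*Combined protocol and SAP*

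**What the plan says.** **The question.** The synopsis introduces Aim 2 with "Though symptoms can be improved for periods up to 6 months, pain symptoms can recur", and section 2.1 adds "The effect of repeated treatments of hylan G-F 20 will be studied". The synopsis lists the aim as secondary and section 2.1 as primary. Two other places presuppose earlier relief. The synopsis Rationale describes retreatment as a way of keeping patients in an acceptable symptom state. Section 13, under Secondary Outcomes, ties the subsequent injection to recurring pain.

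**Who may be re-injected.** The synopsis Study Design row, section 3.1 and section 7.4.1 say: "Patients may return for retreatment of hylan G-F 20 if symptoms recur after at least 4 months following their previous injection". The measurable part of that rule is the current level on WOMAC items: "Inclusion criteria for pain level is defined by selecting moderate, severe, or extreme on all questions A1, C8, C9, C10 and/or C23". The synopsis rows on test product and on duration of participation say instead: "Patients may return for retreatment as early as 4 months post their prior injection if they meet the retreatment criteria pain levels". These rows name Worst Knee Pain as the measure, give no number, and do not mention recurrence.

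**The analysis.** The synopsis says "For subsequent injections, duration of response over time and median duration of response will be estimated using survival analysis techniques". Section 13 (Analysis of Secondary Endpoints) applies Kaplan-Meier methods to the initial injection and also "in the subset of patients that receive a follow-up injection". Neither place splits that subset by response to the preceding injection. Neither says how a subject who does not respond to the repeat injection enters the curve.

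**The concern.** Whether a further injection restores relief that has been lost is a question about subjects who had relief. Every measurable element of the retreatment rule is elapsed time plus current symptoms, and nothing checks that the preceding injection worked. If subjects who never improved come back at four months, they enter the same Kaplan-Meier curve as relapsers. The repeat-injection result then depends partly on who returned. A repeat injection that works as well as the first in relapsers could look clearly worse in the pooled figure, and that could be misread as loss of effect on repetition.

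**Working it through.** **1. The plan's own figures.** The documents give no figure for the repeat-injection analysis. The nearest is the planning response rate of 65%, with stated power of 92% at n = 120. It reproduces: the 95% Wilson lower limit exceeds 0.50 from 71 responders upward, and the binomial probability of at least 71 of 120 at 65% is 92.3%. I use 65% as the first-injection response rate below.

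At that rate, non-responders number 0.35 × 150 = 52.5, or 0.35 × 120 = 42 after the plan's 20% dropout. Under section 13's definition (score of 3 or less throughout six months) these are upper bounds on never-improvers, because a subject who improves and relapses at month 4 is also a non-responder.

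**2. Share of never-responders among the re-injected.** Let p be the first response rate, r the fraction of responders later re-injected, and u the fraction of never-responders re-injected.

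Share = (1 − p)u / [(1 − p)u + p·r]

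Assumed, not from the documents: r = 0.6 to 0.8 and u = 0.5 to 0.9. With p = 0.65 and 150 subjects:
- relapsers re-injected: 97.5 × 0.6 = 58.5 to 97.5 × 0.8 = 78
- never-responders re-injected: 52.5 × 0.5 = 26.25 to 52.5 × 0.9 = 47.25
- subset size: 58.5 + 26.25 = 84.75 to 78 + 47.25 = 125.25
- lowest share: 26.25 / (26.25 + 78) = 25.2%
- highest share: 47.25 / (47.25 + 58.5) = 44.7%

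Starting from 120 subjects scales the counts by 0.8 and leaves the shares unchanged. Over wider assumptions with 30-35% never improving, the share is 0% if none of them is re-injected, 10-12% if a quarter of them and all others are, 30-35% at equal rates, and 63-68% if all of them but only a quarter of the others are.

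**3. Pooled response after the repeat injection.** Assume 65% in relapsers and 20% in never-responders:

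Pooled = 0.65 × (1 − share) + 0.20 × share = 0.65 − 0.45 × share

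| Never-responder share | Pooled response |
|---|---|
| 0% | 65% |
| 25.2% | 53.7% |
| 44.7% | 44.9% |

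The pooled rate falls below 50% once the share exceeds 0.15 / 0.45 = one third. With p = 0.50 the share is 38-60% and the pooled rate 38-48%. If both groups respond at 65%, the pooled rate is 65% at any share.

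**4. Median duration.** This is a separate illustration. Assume relapsers respond at 70%, durations among responders are exponential with median 26 weeks in both groups, and non-responders enter at duration zero. The median is then 26 × log2(pooled response / 0.5).

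| Subset | Pooled response | Median (weeks) |
|---|---|---|
| Relapsers only | 70% | 12.6 |
| 30% never-improvers responding at 50% | 64% | 9.3 |
| 30% never-improvers responding at 38% | 60.4% | 7.1 |
| 30% never-improvers responding at 20% | 55% | 3.6 |

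If only responders entered the curve, the median under these assumptions would be 26 weeks for every mix. The undefined handling of non-responders therefore matters as much as the mix.

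**5. Can earlier response be classified?** Section 9 collects Worst Knee Pain at 6, 12 and 18 weeks after each injection and visit. Four months is about 17 weeks, so the earliest re-injected subjects have only weeks 6 and 12. The synopsis Study Design row and sections 3.1 and 7.4.1 list WOMAC, Lysholm and Tegner for the same contacts.

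**The case against.** The best reply is that the plan's stated re-injected population is relapsers. The Study Design row, sections 3.1 and 7.4.1, the Rationale and section 13 all speak of recurrence or of maintaining relief, and read literally they keep never-improvers out. Subjects without benefit may also leave for lack of efficacy, a route that section 13 recognises. This stands as far as it goes: a reader might infer that the subset is certain to contain never-improvers, and the documents do not show that. They show an undefined criterion, stated inconsistently.

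A reader might also infer that anyone whose pain never fell must qualify at month 4. That does not follow under the WOMAC version. Entry requires Worst Knee Pain of 4-8 and sets no WOMAC threshold, so a subject with unchanged worst pain may score mild on an item and be ineligible. It could follow under the other version, "if they meet the retreatment criteria pain levels for Worst Knee Pain", but that version states no level.

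Third, outcome in everyone re-injected is a legitimate descriptive target. The secondary analyses are confidence intervals without tests, and section 13 promises a detailed SAP. This also stands, and it is why the pooled estimate should be kept. It does not supply the missing split: the recurrence question in Aim 2 is narrower than the pooled set.

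Finally, the re-injection and repeat-response rates above have no source in the documents, and section 13 plans a duration curve for repeat injections, not a response rate. Both points are correct. The figures show only how far the pooled result could move.

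**Conclusion.** The point holds as a gap in definition and analysis. Aim 2 is framed around recurring pain, recurrence is never defined, one version of the rule omits it, and section 13 pools everyone re-injected. The pooled curve and median can therefore differ materially from the relapser result.

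Under the first set of assumptions the gap in response is 11 to 20 percentage points (65% against 54% to 45%). It is zero if no never-improver is re-injected or if both groups respond alike.

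Two stronger readings should be resisted. One is that the pooled figures describe neither group: they are a weighted mixture, close to the relapser value when the never-improver share is small. The other is that the median must collapse to the first contact: that needs both a pooled response below 50% and non-responders entering the curve at about zero duration, which the plan does not state. The primary endpoint is unaffected.

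**What to change.** In section 13 and the synopsis statistics rows:
- Keep the pooled repeat-injection estimate. Also report response and duration after each repeat injection separately for subjects who had a recorded Worst Knee Pain of 3 or less after the preceding injection and then lost it, and for those who did not. Read the recurrence question in Aim 2 from the first group. This is an analysis classification, not a retreatment rule.
- State the time origin and event for duration, and how non-responders to the repeat injection enter the Kaplan-Meier analysis.
- Classify earlier response from the section 9 contacts, noting that only weeks 6 and 12 are available for subjects re-injected at about four months. Reconcile section 9 with the Study Design row and sections 3.1 and 7.4.1 on which instruments those contacts use.
- Reconcile the Study Design row and sections 3.1 and 7.4.1 with the synopsis test-product and duration rows on the retreatment criterion, including whether a subject who never improved is eligible. No clinical rule is proposed here.

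The cost is wording, provided that Worst Knee Pain is in fact collected at the contacts, and wider intervals. On 58 relapsers the 95% half-width is 1.96 × √(0.65 × 0.35 / 58) = 12.3 points, against 1.96 × √(0.25 / 105) = 9.6 points on 105 pooled. The never-responder group would be less precise still at its smallest: 1.96 × √(0.20 × 0.80 / 26) = 15.4 points on 26 subjects.
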